6.3.3 Power

Key analyses addressed in this section include determining:

- i. the association of pneumonia with detection of pathogens in nasopharyngeal specimens
- ii. the statistical precision of estimates for individual pathogen prevalence
- iii. the risk factors associated with pneumonia
- iv. the background prevalence of risk factors in the study population

Case-control analyses will be used to address (i) and (iii), and case-series analyses will be used to address (ii) and (iv).

For case-control analyses, an equal number of cases and controls is assumed. Analyses will be conducted both by site and pooled across sites. Site-specific and between-site analyses will illuminate which etiologies are common globally and which vary in importance depending on geography and local epidemiologic settings.

6.3.3.1 Determine association of pneumonia with detection of pathogens in nasopharyngeal specimens

Many positive test results in NP specimens are likely to represent carriage only and are not indicative of a causal role in the infection. PERCH plans to evaluate the utility of the lab results from NP specimens by comparing the prevalence of pathogens in the cases to that in the controls. This is the first step in a multiple step process for determining the preventable fraction of pneumonia attributable to specific pathogens. Odds of infection given case or control status will determine the strength of inference of 'causality' of NP sample results. If the pathogen is found more frequently in cases than would be expected (i.e., OR>1.0), this would indicate a causal link between pathogen and disease, assuming no bias or confounding. Odds ratios ≤ 1.0 will be considered non-informative and NP results for those pathogens will not be considered when attributing etiology to the cases. Power is calculated to detect clinically meaningful $ORs\geq 2.0$.

Analysis: the proportion positive for a given pathogen will be compared between cases and controls. Power is calculated for detection of differences in proportions equivalent to odds ratios ≥ 2.0 , ruling out a lower bound of OR=1.0.

The hypothesis to be tested is the following:

- ∫ Ho: p₁=p₀
- l Ha: p₁≠p₀
- p₀: Proportion of nasopharyngeal aspirates in which the pathogen is detected in controls
- p₁: Proportion of nasopharyngeal aspirates in which the pathogen is detected in cases

[figure not shown]
For all analyses a 2-sided alpha will be used. However, a 1-sided test would be appropriate for this analysis because ORs<1.0 are not of interest since it is unclear how to use a negative association for a particular pathogen when determining etiologic fraction of the cases. Therefore, a 2-sided alpha is conservative.

[figure not shown]
Dealing with multiple testing: Multiple tests will be performed on multiple specimens to detect up to 30 pathogens for each case. Per test and per specimen, the Bonferroni correction for 30 pathogens given a desired alpha of 0.05 is 0.00167. But analyses will be conducted at each site (analogous to repeating the study 7 times), which will increase the confidence (reduce the Type I error) of the results. As a balance between multiple testing and replication of analyses, the type I error is set to alpha=0.01.

Power: Results of power calculations are presented in the figure below to detect $OR \ge 2.0$, $OR \ge 3.0$, and $OR \ge 5.0$, for various estimates of prevalence of the pathogen in the cases. For pathogens found present in 15% of cases, all sites have at least 80% power to detect $OR \ge 2.0$. Overall, PERCH has 80% power to detect an OR of 2.0 for case prevalences as low as 1% in

[figure not shown]
Version 6.0_15Nov2013

pooled analyses of all 6300 cases, and as low as 1.5% with 5000 cases. This is potentially important for pathogen discovery.

[figure not shown]

(B) 6% pathogen prevalence in the cases

[figure not shown]
(C) 1% pathogen prevalence in the cases

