4.5.1.6 Urine

Urine samples will be collected from cases and controls for two purposes: (i) to examine for the presence or absence of antibiotic activity, a marker of recent administration of antibiotics which might influence the sensitivity of culture-based microbiological techniques and (ii) to be stored for future examination of antigens that determine etiology and relevant urinary biomarkers (e.g. biomarkers of smoke/air pollution exposure and urinary arsenic). Urine will be taken at the

Version 6.0_15Nov2013

earliest opportunity from children admitted as cases, ideally before the first dose of antibiotic therapy. However, antibiotic infusions will not be delayed to obtain a urine sample uncontaminated with hospital-administered antibiotics. If the urine specimen is not obtained by this time, antibiotic administration should begin. The specimen can still be collected and analyzed for detection of antigens.

For infants and young children, urine will be collected into a perineal adhesive bag and transferred to a sterile universal container. Older children may pass urine directly into a sterile universal container. If antibiotics have been given by the nursing or medical staff prior to capturing the specimen then the specimen data collection form will be documented appropriately and the sample container will also be marked. Samples will be taken to the laboratory and stored immediately at 4-8 °C until processed.

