The analysis of Part A would permit construction of the histogram (or pie chart) of the frequency of pathogens, separately for cases and for controls, for any given set of risk factor values.

In Part B, using the cases and the controls we will regress the presence/absence of pneumonia on the indicators of infection and on selected interactions. Each coefficient represents the contribution of that infection (or pair of infections) on the risk of pneumonia. Given the large number of predictors relative to the expected number of pneumonia cases, *we propose to use the LASSO approach* to select a smaller subset of main effects and interactions that best predict case status (i.e. hospitalized pneumonia) (R 1996; Park 2007).

Because the analysis of Part B will be done with case-control data, only the relative odds of pneumonia for each pathogen-specific infection can be estimated. Specifically, we will be estimating for each pathogen and for various co-pathogen pairs the likelihood of infection given that the child has pneumonia compared with the likelihood of infection given that the child does not have pneumonia. Odds ratios that are near or approaching one are interpreted therefore to mean that there was a near equal likelihood of infection among the cases and the controls and no specific evidence that the pathogen was causally associated with pneumonia status.

The lack of association does not mean that the pathogen does not cause pneumonia; it simply means that there is no evidence of a causal association using measurement "M". In other words we are not assessing the relative *risk* of pneumonia given infection, we are only assessing the relative *likelihood* (or odds) of infection given pneumonia status compared with the likelihood of infection given control status. These relative odds values will be applied to the infection prevalences in the first histogram to obtain the histogram of causal effects, given covariates. The LASSO procedure will tend to shrink most regression coefficients in Part B towards 0. This will give the corresponding infections 0 as their estimated causal effect. If this is unsatisfactory, we will use alternatives to the LASSO that shrink less.

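### Protocol 6.3.3.1 drops a pathogen's NP results when its odds ratio is 1.0 or below, with no allowance for sampling error or for detection lost to antibiotics

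*Protocol*

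**What the plan says.** Section 6.3.3.1 compares the proportion of cases and controls with each pathogen in the nasopharynx. An odds ratio above 1.0 is read causally: "this would indicate a causal link between pathogen and disease, assuming no bias or confounding". Odds ratios of 1.0 or below "will be considered non-informative and NP results for those pathogens will not be considered when attributing etiology to the cases". The reason for using one direction only is that "it is unclear how to use a negative association for a particular pathogen when determining etiologic fraction of the cases".

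The same section describes a formal test. "For all analyses a 2-sided alpha will be used"; "As a balance between multiple testing and replication of analyses, the type I error is set to alpha=0.01"; and power is computed for "ruling out a lower bound of OR=1.0". Nothing connects that test to the exclusion sentence. The sentence also does not say whether the odds ratio is crude or adjusted, by site or pooled, or an estimate or a limit.

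Section 6.2.1 (Part B) warns: "The lack of association does not mean that the pathogen does not cause pneumonia". It then plans a Bayesian hierarchical model in which each test result enters with uncertain sensitivity and specificity. Section 4.5.1.6 describes antibiotic activity in urine as "a marker of recent administration of antibiotics which might influence the sensitivity of culture-based microbiological techniques".

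**The concern.** The first two primary objectives, association and attributable fraction, depend on how NP detections are turned into attributed etiology. A hard cut at 1.0 placed ahead of the model has two effects.

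- It treats chance asymmetrically. A null pathogen that happens to fall above 1.0 goes forward, while one that happens to fall below is removed, so the deviations no longer cancel.
- It removes evidence exactly where a causal signal is easiest to hide: an organism that many healthy children carry, and that is detected less often in cases who took antibiotics before admission. *S. pneumoniae*, named in the second objective, is sought by NP culture in both cases and controls (Tables V and VIII).

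Later modelling cannot recover NP results that have already been excluded.

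**Working it through.** **Inputs from the protocol.** Two-sided alpha 0.01, 1:1 allocation and an odds ratio of 2.0 for power (6.3.3 and 6.3.3.1); smallest site 500 cases and 600 controls, total 6300 cases (Table XIV). **Assumed, not in the protocol:** carriage levels, share of cases caused, pre-treated share, loss of detection, and no loss in controls.

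**1. The plan's own figure.** The protocol states at least 80% power at every site for an odds ratio of 2.0 with 15% case prevalence. Control prevalence is then 8.1%. With 500 per group and pooled variance, power = Φ[(0.0689 − 2.576 × 0.0202)/0.0201] = Φ(0.84) = 79.9%. With 600 controls it is 84.4%. The figure reproduces, so the alpha 0.01 test is well defined. No error rate is stated for the exclusion rule.

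**2. Null pathogen (true odds ratio 1), equal groups.**

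- Point-estimate reading: P(estimate > 1) = [1 − P(tie)]/2. At n = 500 and 1% prevalence, (1 − 0.128)/2 = 0.436. At n = 6300 and 30% prevalence, (1 − 0.008)/2 = 0.496.
- Alpha 0.01 reading, upper tail only: 0.01/2 = 0.005.

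**3. True odds ratio 1.5, 500 per group.**

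| Control prevalence | Kept if estimate > 1 | Kept if significant at 0.01 |
|---|---|---|
| 5% | 93.6% | 14.6% |
| 15% | 99.3% | 44.7% |
| 30% | 99.9% | 67.8% |

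The two readings exchange one error for the other, so neither settles the matter.

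**4. Masking of a commonly carried cause.** Let p0 be carriage in controls and e = 0.10 the share of cases caused. Case prevalence is p1 = e + (1 − e)p0. The proportion of case detections that must be lost for the odds ratio to reach 1.0 is L = 1 − p0/p1.

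| p0 | p1 | Odds ratio | L |
|---|---|---|---|
| 70% | 73% | 1.16 | 4.1% |
| 50% | 55% | 1.22 | 9.1% |
| 30% | 37% | 1.37 | 18.9% |

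If a share f of cases is pre-treated and each loses a fraction l of detections, then L = f × l. With p0 = 70%, f = 0.30 and l = 0.50, observed case prevalence is 0.73 × 0.85 = 0.62 and the odds ratio is 0.70.

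At the other end of the range, masking a true odds ratio of 2.0 needs L of 47.5%, 42.5%, 35% or 20% at control prevalence 5%, 15%, 30% or 60%. With 30% prevalence, f = 0.25 and l = 0.60, the observed odds ratio is still 1.51.

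**5. Chance alone.** For the 70% carriage example at a 500/600 site, the standard error is √(0.73 × 0.27/500 + 0.70 × 0.30/600) = 0.0273. Then z = 0.03/0.0273 = 1.10, and the estimate falls at or below 1.0 in 13.6% of samples. With 6300 per group the standard error is √[(0.73 × 0.27 + 0.70 × 0.30)/6300] = 0.0080, z is about 3.7, and chance loss is negligible. Masking, by contrast, does not shrink with sample size.

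**The case against.** The strongest reply has four parts.

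- **The criterion is not stated.** The section sets a two-sided 0.01 test, and if that governs, null pathogens pass 0.5% of the time. This is correct, and the 44-50% figure belongs to the literal reading only. But the exclusion sentence does not refer to the test, and the test reading loses more true causes of modest size.
- **Passing is not attribution.** The section calls the comparison a first step. Section 6.2.1 reads odds ratios near one as no specific evidence of causation, and the LASSO would set many weak effects to zero. This stands. A reader might infer that about half of non-causal pathogens are credited as causes, or might add up the upward deviations: for 15 assumed null pathogens at 10% carriage and a 500/600 site, 0.0080 × 15 = 12% of pneumonia. The documents support neither. The total rests on an assumed count and an attribution formula the protocol does not contain, and it skips the later steps. Those steps are not a full safeguard either, since 6.2.1 allows replacing the LASSO with methods that shrink less.
- **Only NP results are dropped.** Pneumococcus is also sought in blood, induced sputum and, where collected, lung aspirate and pleural fluid. This stands, so it would be wrong to infer that the rule removes a pathogen as a cause. It also softens the conflict with 6.2.1: calling a result uninformative is not calling the pathogen harmless.
- **Antibiotics are partly handled.** Respiratory specimens are meant to precede antibiotics, antibiotic use is a listed risk factor for infection, pre-treated children are a likely sub-group, and the acknowledged effect concerns culture, whereas most NP testing is PCR. These points limit the scope. They do not reach the cut, which makes no allowance for exposure before hospital, and pneumococcus is cultured from NP swabs.

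**Conclusion.** The point holds as a badly fixed decision rule. The cut at 1.0 is one-directional and has no stated precision or adjustment. On the literal reading it passes 44-50% of null pathogens to later steps. On the alpha 0.01 reading it passes about 0.5%, but keeps a true odds ratio of 1.5 at a 500-case site only 15-68% of the time, for control prevalence 5-30%.

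For a heavily carried cause a small differential loss of detection is enough to remove its NP evidence: about 4% at 70% carriage with 10% of cases caused, rising to 19% at 30% carriage. That antibiotic masking will occur is not shown. It is a plausible mechanism of unknown size, and a cause with an odds ratio of 2.0 would need a loss of 20-48% over control prevalences of 60% down to 5%.

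The rule also sits badly with the caution in 6.2.1 and with a Bayesian model built to use imperfect results with their uncertainty.

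**What to change.** - In 6.3.3.1, delete the exclusion of NP results at odds ratios of 1.0 or below.
- State that every pathogen's NP results enter the Bayesian model of 6.2.1 with the full uncertainty of the odds ratio, including values at or below 1.0.
- Estimate bacterial NP odds ratios adjusted for, or stratified by, the antibiotic-activity results already planned in cases and controls (serum in Tables IX and X; urine on a subset).

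Do not replace the cut with significance alone, which loses modest true effects as step 3 shows. Nor should exclusion require an upper limit below 1.0: with a 95% interval that would retain about 97.5% of null pathogens.

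The cost is revised wording and some additional modelling. No new data are needed. Some etiologic fractions will have wider intervals.

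### Alpha is relaxed from 0.00167 to 0.01 because seven site analyses are said to reduce Type I error, but no cross-site agreement rule is stated that would make this so

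*Protocol*

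**What the plan says.** Protocol 6.3.3.1 sets the threshold for comparing pathogen detection in nasopharyngeal specimens between cases and controls. It describes the multiplicity as "Multiple tests will be performed on multiple specimens to detect up to 30 pathogens for each case" and states that "the Bonferroni correction for 30 pathogens given a desired alpha of 0.05 is 0.00167". It then argues that the site analyses are "analogous to repeating the study 7 times), which will increase the confidence (reduce the Type I error) of the results", and concludes: "As a balance between multiple testing and replication of analyses, the type I error is set to alpha=0.01".

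Three further statements bear on the reading:

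- Sidedness: "For all analyses a 2-sided alpha will be used". Only odds ratios above 1 count as evidence for a pathogen. For those at or below 1, "NP results for those pathogens will not be considered when attributing etiology to the cases".
- Scope of the analyses (6.3.3): "Analyses will be conducted both by site and pooled across sites". The site analyses are meant to show which etiologies are common everywhere and which depend on geography.
- Role of the comparison: "This is the first step in a multiple step process for determining the preventable fraction of pneumonia attributable to specific pathogens".

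Neither 6.3.3 nor 6.3.3.1 requires a pathogen to be significant at two or more sites, or both pooled and at a site.

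**The concern.** The six-fold relaxation from 0.00167 to 0.01 rests on a single reason, and that reason does not hold as written. Repeating a family of tests in seven independent samples lowers the false-positive rate only when the claim requires agreement between samples. If any site may contribute a finding by itself, which the interest in geographic differences allows, the repetition enlarges the family from 30 to 30 × 7 = 210 tests.

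At stake are the error rate of the screen and the sample-size argument. The protocol names 5% over 30 pathogens as its target and then sets a threshold that does not deliver it. The power statements in 6.3.3.1, including the one offered as important for pathogen discovery, use the relaxed value. A reader is therefore given favourable power and a claim of error control that cannot both be relied on.

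**Working it through.** **Inputs.** All are from the Protocol: 30 pathogens, desired alpha 0.05, adopted two-sided alpha 0.01 and OR 2.0 (6.3.3.1); 1:1 cases to controls (6.3.3); seven sites, smallest target 500 cases, total 6300 cases (Table XIV).

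**1. The plan's threshold.** 0.05/30 = 0.00167. This reproduces.

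**2. Family-wise error with all nulls true and tests independent.** The formula is 1 − (1 − a)^m. A false rejection in either direction has a = 0.01. A false pathogen under the protocol's rule needs OR>1, so a = 0.005.

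| Family | Either direction | OR>1 only |
|---|---|---|
| 30 pooled tests | 1 − 0.99^30 = 26.0% | 1 − 0.995^30 = 14.0% |
| 210 site tests | 1 − 0.99^210 = 87.9% | 1 − 0.995^210 = 65.1% |

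The expected number of false OR>1 findings is 30 × 0.005 = 0.15 pooled and 210 × 0.005 = 1.05 over sites. At 0.00167 the 30 pooled tests give 4.9% in either direction and 2.5% for OR>1. Setting 14% against 5% is therefore the comparison more generous to the plan.

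**3. Sensitivity, OR>1 only.**

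- Only 15 of 30 pathogens null: 1 − 0.995^15 = 7.2% pooled; 1 − 0.995^105 = 40.9% at any site.
- All 30 null, correlation 0.5 between pathogens within a site (20,000 simulated sets of z-scores): about 8% pooled and 43% at any site.
- Both together (15 nulls, correlation 0.5): pooled 1 − ∫φ(u)Φ((2.576 − √0.5·u)/√0.5)^15 du = 4.9%; any site 1 − (1 − 0.0487)^7 = 29.5%.

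**4. What an agreement rule would deliver.** With seven independent sites at two-sided 0.01, the null probability of significance at two or more sites is 0.00203 per pathogen, so 1 − (1 − 0.00203)^30 = 5.9% over 30. Requiring OR>1 at both sites (0.005 each) gives 0.000516 per pathogen and 1 − (1 − 0.000516)^30 = 1.5%.

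**5. Power.** The control proportion p0 follows from case prevalence p1 and OR 2: odds0 = [p1/(1 − p1)]/2. With p̄ = (p1 + p0)/2,

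power = Φ{[(p1 − p0)√n − z√(2p̄(1 − p̄))] / √[p1(1 − p1) + p0(1 − p0)]},

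where z = 2.576 at 0.01 and 3.144 at 0.00167.

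| n per group | p1 | p0 | Stated in 6.3.3.1 | At 0.01 | At 0.00167 |
|---|---|---|---|---|---|
| 500 | 15% | 8.11% | at least 80% | 79.9% | 60.5% |
| 5000 | 1.5% | from OR 2 | 80% | 82.9% | 64.8% |
| 6300 | 1% | 0.50% | 80% | 74.5% | 53.6% |

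The first two stated figures reproduce. The third does not at 1:1; with the 7200 controls of Table XIV it is 78.3%. At 0.00167, 80% power at 15% prevalence needs 682 per group. Sites with a target of 700 still reach it (81.5%); only the 500-case site falls short at target enrolment.

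**The case against.** Three points on the other side have force.

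First, replication can justify a looser per-test alpha. Step 4 shows that 0.01 with agreement at two or more sites would nearly meet or comfortably beat 5%. A reader might infer that the reasoning is simply backwards. The documents do not support that: the idea is sound but lacks the rule that would make it work. The rule might be left to a statistical analysis plan, but the protocol does not defer it. It asserts the reduction as a fact and fixes alpha from it.

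Second, a reader might take 26% and 88% as the chance of declaring a false pathogen. Those figures count both directions, and the protocol discards odds ratios at or below 1. They also assume that all 30 pathogens are null, although the Background treats several as established causes. This objection stands, and the OR>1 figures are the ones to use.

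Third, a reader might infer that every pathogen finding rests on the 0.01 threshold. It does not. The value appears only in the power section. The analysis plan in 6.2.1, to which 6.2.2 refers, uses LASSO selection, a measurement-error model and Bayesian hierarchical estimation, with no such cut-off. Section 6.3.3.1 calls the comparison a first step and words its exclusion by the size of the odds ratio, not by a p-value. This also stands and limits the consequence.

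Strict 5% family-wise control is not the only reasonable choice for a screen. A looser threshold could be defended openly as such, but the protocol names 5% and gives a different reason for leaving it.

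**Conclusion.** The concern holds in limited form. The stated reason for moving from 0.00167 to 0.01 fails without a cross-site agreement rule, and the desired 5% is not delivered. Under independence with all nulls true, the chance of at least one false OR>1 finding is about 14% pooled and 65% at any site. Correlation of 0.5, or only 15 true nulls, brings this to about 7-8% and 41-43%. Only with both reliefs together does the pooled figure reach about 5%, and the any-site figure is then still near 30%. The correlation and the number of true nulls are assumptions, since the protocol gives neither.

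The effect is confined to the first-step nasopharyngeal screen and the power statements built on 0.01. A false positive there is not yet a final etiologic attribution. The point should be fixed, but it does not undermine the primary analysis. The failure of the 80% power claim at 1% prevalence to reproduce even at 0.01 is a separate matter, to be settled in the same revision.

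**What to change.** Strike the sentence that credits the site analyses with reducing Type I error. Name the family of tests and the error rate to be controlled. Then choose one of two routes:

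- Control 5% over the roughly 30 pooled tests, for example by Holm, and read site results as estimates or as evidence of heterogeneity.
- Keep 0.01 and write the concordance rule that justifies it, for example OR>1 with p<0.01 at two or more of the seven sites (about 1.5% over 30 pathogens).

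Restate power under the rule chosen. The figures at 0.00167 in the working apply to a fixed Bonferroni threshold; Holm is at least as powerful. A concordance rule needs its own calculation, because power then depends on the site sample sizes.

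The cost is wording and less favourable stated power, chiefly for rare pathogens and the smallest site. No design change or new data collection is needed.

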6.3.1 Sample size

The target enrollment sample size was based on a series of power calculations and incorporates the need to capture seasonal variations in risk factors for pneumonia and in disease incidence, as well as the cost of testing each subject enrolled. The sample size calculations permit sufficient power to undertake site-specific analyses with a reasonable degree of precision, to conduct sub-analyses of pooled data while controlling for age, season, and site, and to support the identification of novel pathogens.

Cases: Small sites (Bamako, Thailand) will enroll all eligible cases. At the other large sites, sampling of cases will be implemented to restrict the target number of PERCH cases to 6300.

Controls: The target number of controls is based on a minimum background enrollment rate of 25 per month (i.e., 600 over 2 years per site) combined with a 1:1 case:control ratio when monthly case enrollment exceeds the minimum control background rate. For large sites, we anticipate that the overall case:control ratio will be approximately 1:1. For small sites, the overall ratio is anticipated to be slightly higher. For Lusaka and Soweto (i.e., sites with high HIV prevalence), an additional HIV+ control group will be added assuming a 1:1 ratio with the number of enrolled HIV+ cases.

Table XIV. Target case and control enrollment by site and total					
Site	Cases	Controls			
		Community	HIV+ controls		
		Controls			
Bamako, Mali	700	900			
Basse, The Gambia	700	900			
Sa Kaeo/Nakhon Phanom, Thailand	500	600			
Soweto/Johannesburg, South Africa	1200	800	400		
Dhaka, Bangladesh	1200	1200			
Kilifi, Kenya	1200	1200			
Lusaka, Zambia	800	850	350		
Total	6300	7	200		

While PERCH has set a target of 6300 cases to be enrolled, the number actually available may range from 5000-7000. This is due either to losses in data for analysis or higher than projected numbers of cases consenting at some sites. Losses may result from inability to collect and test all specimens, ineligibility due to severe pneumonia signs resolving upon administration of bronchodilators, changes in procedures over time that result in excluding some cases from analysis, and because some sites may not be prepared to start in Jan 2011 (due to minor site capacity development or IRB processes) and thus may not achieve a full 2 years enrollment before the study ends. To account for these potential losses, a low (70%) estimate is provided below.

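### The stated 80% pooled power for OR 2.0 at 1% case prevalence with 6300 cases is about 74.5% on the protocol's own inputs; 80% is reached at about 1.1%

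*Protocol*

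**What the plan says.** The power statements are in Protocol section 6.3.3.1. For the pooled analysis: "Overall, PERCH has 80% power to detect an OR of 2.0 for case prevalences as low as 1" per cent with all 6300 cases, with a second claim of 1.5% prevalence for 5000 cases. For single sites: "For pathogens found present in 15% of cases, all sites have at least 80% power to detect" an odds ratio of 2.0 or more.

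The inputs are also given. The analysis is one in which "the proportion positive for a given pathogen will be compared between cases and controls". On the error rate: "For all analyses a 2-sided alpha will be used", and after weighing multiplicity against replication across sites, "the type I error is set to alpha=0.01". Section 6.3.3 adds: "For case-control analyses, an equal number of cases and controls is assumed".

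Section 6.3.1 gives a target of 6300 cases and says that the number available may lie between 5000 and 7000. It then lists reasons for loss: "To account for these potential losses, a low (70%) estimate is provided below". Table XV puts that estimate at 350 cases for Thailand, 490 each for Mali and The Gambia, 560 for Zambia, 840 for each of the other three sites, and 4,410 in total.

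**The concern.** A stated power should follow from the stated inputs. The pooled figure at 1% does not, although its neighbours do. The protocol describes the low-prevalence result as potentially important for pathogen discovery, and section 6.3.3.1 presents this case-control comparison as the first step towards attributable fractions. A reader relying on the sentence would put the chance of missing a true odds ratio of 2.0 at 1% prevalence at 1 in 5, when it is about 1 in 4. The same section calls the two-sided alpha conservative, so the reader would also assume that the 80% already includes that cost.

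The site sentence raises a smaller question. It does not say which enrolment it assumes, while the protocol tabulates both a target and a low estimate for every site.

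**Working it through.** **Inputs.** Two-sided alpha 0.01 (z = 2.5758), 1:1 groups, OR 2.0, and case prevalence p1 and number per group n as stated. Control prevalence p0 follows from odds(p0) = odds(p1)/2.

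**Formula.** Normal-approximation test of two proportions with pooled variance under the null. With d = p1 − p0 and p̄ = (p1 + p0)/2:

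- SE0 = √[2p̄(1 − p̄)/n]
- SE1 = √{[p1(1 − p1) + p0(1 − p0)]/n}
- power = Φ[(d − z·SE0)/SE1]

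**Step 1: the claims that reproduce.**

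- 1.5%, n = 5000: p0 = 0.007557, d = 0.007443, SE0 = 0.0021120, SE1 = 0.0021107. (0.007443 − 0.005440)/0.0021107 = 0.949, so power is 82.9%. 80% needs 4,700 per group, so the claim is met.
- 15%, n = 500 (Thailand, the smallest site, at target): p0 = 0.08108, d = 0.06892, SE0 = 0.020218, SE1 = 0.020100. (0.06892 − 0.05208)/0.020100 = 0.838, so power is 79.9%, in effect the stated 80%.

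**Step 2: the claim that does not.**

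- 1%, n = 6300: p0 = 0.005025, d = 0.004975, SE0 = 0.0015385, SE1 = 0.0015379. (0.004975 − 0.003963)/0.0015379 = 0.658, so power is **74.5%**.

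**Step 3: does another method or reading give 80%?** All rows use 1% prevalence and 6300 cases.

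| Calculation | Power |
|---|---|
| Unpooled variance | 74.5% |
| Arcsine | 75.9% |
| Log odds ratio (Wald) | 72.4% |
| Continuity-corrected | 71.1% |
| Exact chi-square | 75.2% |
| Fisher exact | 72.2% |
| 6450 community controls instead of 1:1 | 75.2% |
| All 7200 controls instead of 1:1 | 78.3% |
| One-sided alpha 0.01 | 81.8% |

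The first six rows keep the stated inputs and span 71.1% to 75.9%. The last three depart from them. Only the one-sided test passes 80%, and the protocol specifies a two-sided alpha. The 7200 controls include 750 HIV-infected controls recruited separately at two sites (400 + 350, Table XIV).

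**Step 4: what delivers 80%.** At 1% prevalence, about 7,036 per group. With n fixed, the case prevalence needed is 1.12% at 6300, 1.41% at 5000 and 1.60% at 4,410 per group.

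**Step 5: sites at 15% prevalence.**

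| Site | Target cases: power at 1:1 | 70% estimate: power at 1:1 | 70% cases, planned target controls kept |
|---|---|---|---|
| Thailand | 500: 79.9% | 350: 60.9% | 350 vs 600: 75.8% |
| Mali; The Gambia | 700: 92.9% | 490: 78.9% | 490 vs 900: 90.7% |
| Zambia | above 80% | 560: 85.0% | – |
| South Africa; Bangladesh; Kenya | above 80% | 840: 96.8% | – |

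With Thailand's 600 planned controls and the full 500 cases, power is 84.4%. For Mali and The Gambia at 490 per group, the exact chi-square calculation gives 79.5%.

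**The case against.** The best defence of the pooled figure is that the shortfall is small. It amounts to 1% in place of 1.12%, which looks like rounding down. The target control total exceeds the case total, and counting every control brings power to 78.3%. The protocol also hedges itself by giving the 5000-case figure, which is correct, and section 6.3.1 attributes the sample size to precision by site, seasonality and testing cost as well as to power. All of that stands as to importance. It does not rescue the sentence, which gives 80% at 1% while the text fixes equal groups and a two-sided alpha.

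Three stronger readings are tempting, and the documents do not support them.

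- **The all-sites claim is wrong, failing at three sites.** The protocol does not extend that sentence to the 70% estimate, and at target it reproduces. Under the 70% estimate only Thailand clearly falls short. Mali and The Gambia are about one point under 80% at 1:1. They exceed it with their planned controls, and also if those are scaled to 70% (490 vs 630 gives 85.0%).
- **The protocol gives no power at the reduced sizes, or its power figure is wrong.** The power curves could not be seen in the text available to me. Section 6.3 says that a range of sample sizes is covered, so neither statement can be shown.
- **Pathogen discovery depends on the 1% figure.** The protocol says only that it is potentially important for that purpose.

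**Conclusion.** The pooled statement is wrong as written: about 74.5% power, not 80%, for OR 2.0 at 1% case prevalence with 6300 cases and 6300 controls at two-sided alpha 0.01. The gap is about 5.5 points, or equivalently 0.12 percentage points of prevalence. The result rests only on inputs that the protocol states and is stable across six standard calculations (71.1% to 75.9%). The claim for 5000 cases is correct.

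The site sentence is not an arithmetic error. It holds at target enrolment and lacks that qualification. The qualification matters mainly for Thailand, where 500 is both the target and the estimated number of eligible, consenting cases (Table XIII). There is therefore no reserve, and power at 70% is 60.9% at 1:1 or 75.8% with 600 controls. These site figures assume 15% case prevalence, OR 2.0 and unadjusted comparisons.

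Nothing here shows that the sample size should change.

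**What to change.** In section 6.3.3.1, replace the pooled sentence in one of two ways:

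- State 80% power at OR 2.0 for case prevalences of about 1.1% or more with 6300 cases and about 1.4% or more with 5000. Ideally add about 1.6% at the 70% total of 4,410.
- Keep 1% and state about 74.5% power.

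In the site sentence, add that it applies at target enrolment. A clause giving Thailand's power under the 70% estimate (about 61% at 1:1, about 76% with 600 controls), and noting that Mali and The Gambia are borderline (about 79% at 1:1), would complete it.

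The authors should check that the plotted 1% panel agrees with the corrected text. The cost is a few words of text. Enrolment, alpha and analysis are unaffected, and the only consequence is a slightly less favourable stated power.
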